8.6 Bleeding episodes

All bleeding episodes and treatments with N8-GP must be recorded in the eCRF by the investigator or in the eDiary by the patient's parent(s)/LAR(s).

Protocol v 1 | 61 of 114

Protocol
Trial ID: NN7088-3908

CONFIDENTIAL

Date: 04 November 2013 | Novo Nordisk
Version: 1.0

Final

62 of 114

UTN: U1111-1148-1897

EudraCT No.: 2013-004025-88

CONFIDENTIAL

CONFIDENTIAL

Status:

Page:

8.6.1 Assessments of bleeding episodes and treatment response

The severity of bleeding episodes is defined as

- Mild/moderate: Bleeding episodes that are uncomplicated joint bleeding episodes, muscular bleeding episodes without compartment syndrome, mucosal- or subcutaneous bleeding episodes. These bleeding episodes can be treated at home after V2 and details of the bleeding episodes should be entered in the eDiary by the patient's parent(s)/LAR(s).
- Severe: All intracranial, retroperitoneal, iliopsoas and neck bleeding episodes must be categorised as severe. Muscle bleeding episodes with compartment syndrome and/or bleeding episodes associated with a significant decrease in the haemoglobin level (>3g/dl) should also be reported as severe (it is the investigators decision if haemoglobin measurements should be performed). The investigator must be contacted in case of a severe bleeding episode.

In case of treatment requiring bleeding episode outside the trial site opening hours prior to 2 EDs the patient must be treated according to local procedures.

Bleeding Episode – information to be collected

Information about bleeding episodes prior to the 2 ED (V2) should always be recorded in eCRF. In case the patient is treated outside the trial site the trial site should be informed in case of a bleeding episode and the details hereof. After 2 EDs bleeding episodes must be recorded either in the eDiary (if treated at home) or in the eCRF (if treated at the trial site), see Section 12.3.

- Date and time the bleeding episode started
- Date and time the bleeding episode stopped
- Cause of the bleeding episode
 - i.e. spontaneous, traumatic or due to surgery
- Anatomical location of bleeding episodes
- Treatment of bleeding episodes
 - Amount, and time of each dose of N8-GP
- Haemostatic response assessed by the 4-point scale defined in Table 8–1

Table 8–1 4-point scale

Classification	Description
Excellent	Abrupt pain relief and/or clear improvement in objective signs of bleeding within approximately 8 hours after a single injection
Good	Definite pain relief and/or improvement in signs of bleeding within approximately 8 hours after a single injection, but possibly requiring more than

Protocol v 1 | 62 of 114

Protocol Date: 04 November 2013 Novo Nordisk
Trial ID: NN7088-3908 Version: 1.0

That ID: NN/088-3908
UTN: U1111-1148-1897
EudraCT No.: 2013-004025-88

CONFIDENTIAL
Status: Final
Page: 63 of 114

Classification	Description
	one injection for complete resolution
Moderate	Probable or slight beneficial effect within approximately 8 hours after the first injection, but usually requiring more than one injection
None	No improvement, or worsening of symptoms

Re-bleed

Classification of re-bleed will be performed at the time of the statistical analysis, according to the following criteria:

• A re-bleed is defined as a new bleed within 72 hours after stopping of a previous bleed at the same or a subset of the same anatomical locations

If a bleeding episode occurs in the same location later than 72 hours after stopping the treatment it is considered as a new bleeding episode.

8.7 Surgery

Preventive N8-GP treatment before minor surgery including placement or removal of central venous access port can be performed within this trial at the investigator's discretion according to local guidelines. A dose of 40-75 U/Kg N8-GP prior to minor surgery is recommended to prevent perioperative bleeding episodes, see Table 5–1. Major surgeries are only allowed after 50 EDs and when the result from the pathfinderTM3 (NN7088-3860) is available, see Section 5.3.4.

Preventive N8-GP treatment prior to surgery should be captured in eCRF or in the eDiary.

8.7.1 Minor surgery

Definition of minor surgery, see Section 5.3.4.

For minor surgery the following should be recorded:

- Date, time and volume of preventive dose before surgery
- Type of surgery
- Indication for surgery
- Date of surgery
- Start time of surgery

8.7.2 Major surgery

Definition of major surgery, see Section 5.3.4.

FVIII inhibitor sample should be taken prior to surgery and analysed at the central laboratory.

Protocol v 1 | 63 of 114

04 November 2013 | **Novo Nordisk** Protocol Date: Trial ID: NN7088-3908 Version: 1.0 UTN: U1111-1148-1897 Final Status: EudraCT No.: 2013-004025-88 64 of 114

Page:

For major surgery the following should be recorded in the eCRF:

- Date, time and volume of preventive dose before surgery
- Type of surgery
- Indication for surgery
- Date of surgery
- Start and stop time of surgery
- Clinical evaluation of haemostatic response, see Table 8–1
- Clinical narrative of the procedure

Injections with N8-GP administered after surgery has been completed should be reported either in the eCRF (injections administered at site) or in the eDiary (injections administered at home), see Section 12.3

8.8 Training and reminders

8.8.1 Trial card dispensing

At V0 the patient's parent(s)/LAR(s) will receive a trial card stating that the patient is participating in a clinical trial. Telephone numbers and contact persons at the trial site will be listed.

8.8.2 Home treatment training

Home treatment training with administration of N8-GP can start after administrations of the first dose at the trial site (see Section 8.1.12), and should continue until the patient's parent(s)/LAR(s) are comfortable with the reconstitution and administration process.

A home treatment guide for the reconstitution and administration process will be available as handsout for the patient's parent(s)/LAR(s). Training in reconstitution and administration must be performed until parent(s)/LAR(s) feel comfortable in handling the treatment. The training must be documented in the medical records.

All patient's parent(s)/LAR(s) must be carefully instructed in recognising and dealing with signs and symptoms of an anaphylactic reaction. This includes knowledge of which medical facility to contact in this situation

If the patient does not follow the planned dosing schedule, the investigator must retrain the patient's parent(s)/LAR(s).

Protocol v 1 64 of 114 Protocol Trial ID: NN7088-3908 Date: 04 November 2013 Version: 1.0 Novo Nordisk

Status:

Page:

Final

65 of 114

UTN: U1111-1148-1897 EudraCT No.: 2013-004025-88

8.8.3

Electronic diary (eDiary)

Pre-prophylaxis treatment, prophylaxis treatment and bleeding episodes should be recorded in the eCRF for the first 2 EDs. When the first 2 EDs have been administered, the data will be captured either in eCRF or eDiary according to Section 12.3.

Parent(s)/LAR(s) should be trained in using the eDiary before or when they receive the eDiary. If needed the training must be repeated until the parent(s)/LAR(s) use the eDiary as intended.

It will be the responsibility of the investigator to assess the eDiary data throughout the conduct of the trial and to ensure entry compliance.

During the home treatment period the patient's parent(s)/LAR(s) must ensure that all preprophylaxis and prophylactic home treatment, bleeding episodes, treatment of bleeding episodes as well as haemostatic evaluation of the treatment of bleeding episodes are captured in the eDiary.

8.8.3.1 eDiary dispensing and collection

The eDiary will be dispensed to the patient's parent(s)/LAR(s) at V2.

For details regarding patient's eDiary, please refer to Section 12.3.

For patients completing the trial or in case of withdrawal, the eDiary will be collected at the EOT visit.

8.8.4 Contact between the investigator/medically qualified person and the patient

The investigator and/or medically qualified person must establish contact with the patient's parent(s)/LAR(s) at least every 12 weeks \pm 1 week, if site visits are more than 3 months apart, either by visits at the trial site or other contact e.g. telephone calls. All contact must be captured in eCRF.

The patient and patient's parent(s)/LAR(s) should be notified that they will be contacted according to the protocol.

The communication will focus on the well-being of the patient, including enquiry to all AEs, and any medical treatment (including treatment of bleeding episodes) since the last contact. The investigator/medically qualified person should not suggest specific AEs to patient's parent(s)/LAR(s), but should inquire e.g. "how is your child doing?" and "has your child had any medical problems since the last contact?", and "have you remembered to enter all treatment in the eDiary?".

Protocol v 1 | 65 of 114

EudraCT No.: 2013-004025-88

 Protocol
 Date:
 04 November 2013
 Novo Nordisk

 Trial ID: NN7088-3908
 Version:
 1.0

 UTN: U1111-1148-1897
 Status:
 Final

Page:

66 of 114

The expiry date of the drug that the patient has received should be checked by the site staff before the patient's next visit to determine if an extra dispensing is relevant and to inform the patient of which unused vials to return to the site.

All attempts to contact the patient's parent(s)/LAR(s) must be documented in a source document. If a successful contact cannot be made after 3 documented attempts, no further attempts are required. If the patient's parent(s)/LAR(s) have withdrawn consent, this must be documented.

At each contact the investigator will at a minimum capture/evaluate

- Assessment of bleeding episodes
- Adverse events
- Concomitant Medication
- eDiary compliance
- N8-GP administration compliance

8.8.5 Interactive voice/web response system

Please refer to Section 10 regarding the IV/WRS.

For details on how to use the IV/WRS, please refer to the trial specific IV/WRS user documents provided to the trial site.

8.9 Patient compliance

Throughout the trial the investigator will remind the patient's parent(s)/LAR(s) to follow the trial procedures and requirements to ensure patient compliance. If a patient is found to be non-compliant, the investigator will remind the patient's parent(s)/LAR(s) of the importance of following the instructions given including taking the trial products as described.

Assessment of patient compliance with protocol procedures for determination of continuation of the trial will be done by the investigator's discretion.

Failure to comply with scheduled visits and N8-GP administration may result in withdrawal in accordance with the protocol withdrawal criteria, see Section 6.4.

Treatment with FVIII concentrates, other than N8-GP, during the trial is not allowed and violation of this may lead to withdrawal due to non-compliance (please refer to Section 8.2.4). Regarding bypassing agents, see Section 8.2.3.

Protocol v 1 | 66 of 114

Compliance with N8-GP treatment must be addressed at each visit. Compliance check includes a cross check between number of injections recorded in eDiary, expected number of doses and the used/returned vials.

Protocol v 1 | 67 of 114

Protocol Date: 04 November 2013 Novo Nordisk
Trial ID: NN7088-3908 Version: 1.0

 Trial ID: NN7088-3908
 Version:
 1.0

 UTN: U1111-1148-1897
 Status:
 Final

 EudraCT No.: 2013-004025-88
 Page:
 68 of 114

9 Trial supplies

Trial supplies comprise trial product and auxiliary supplies. Additional details regarding trial supplies can be found in the Trial Material Manual (TMM) and Handling instruction.

Trial product must not be dispensed to any person not included in the trial (excluding patient's parent(s)/LAR(s)).

Auxiliary supplies comprise supplies other than trial product, e.g. needles and syringes.

9.1 Trial product

The following trial product will be provided by Novo Nordisk, Denmark:

Table 9–1 Trial Product

Trial product	Strength	Dosage form	Route of administration
N8-GP (turoctocog alfa pegol)	 500 U/vial, 53μg/vial 2000 U/vial, 211μg/vial 	Freeze-dried Powder for solution for injection	i.v. injection

N8-GP is supplied as a sterile freeze-dried powder for solution for injection in single use vials with a nominal content of 2000 U/vial or 500 U/vial to be reconstituted with 4.3 mL 0.9% Sodium Chloride Solution. After reconstitution each vial contains 500 U/mL or 125 U/mL N8-GP, respectively. The reconstituted solution is colourless and clear to almost-clear with a pH of 6.9. The reconstituted solution must not be diluted further. Trial product must not be used if it does not appear colourless and clear to almost-clear.

After reconstitution the appropriate volume of the vials will be drawn into a syringe. The content of several vials may be combined in one syringe. N8-GP may not be added to or mixed with any other material.

Administration of the appropriate volume of N8-GP will be given as i.v. bolus injection over approximately 2 minutes (from start to completion of injection).

The investigator must explain to the patient's parent(s)/LAR(s) the injection process of N8-GP at home.

Protocol v 1 | 68 of 114

EudraCT No.: 2013-004025-88

Protocol
Trial ID: NN7088-3908
UTN: U1111-1148-1897

Date: 04 November 2013 | Novo Nordisk
Version: 1.0
Status: Final

Page:

69 of 114

The maximum dose to be administered to a patient within 24 hours is 200 U/Kg, with a maximum individual dose of 75 U/Kg. These doses are only relevant in case of trauma, severe bleedings or surgery.

Novo Nordisk will not supply any Non Investigational Medical Products (NIMPs).

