5.3.3 Treatment of bleeding episodes

Patient's parent(s)/LAR(s) will be instructed by the trial site on how to treat a bleeding episode at home and record in the electronic diary (eDiary). Treatment requiring bleeding episodes should immediately (i.e., when the patient experiences the first clinical symptoms of a bleeding episode) be treated with N8-GP at doses of 20-75 U/Kg bw, depending on severity and location of the bleeding episode, see Table 5–1. For treatment of severe/life-threatening bleeding episodes administration of higher doses of N8-GP is permitted at the investigators discretion. For recommended dose levels see Table 5–1.

of 114 Protocol v 1 29

Thai ID: NN/088-3908
UTN: U1111-1148-1897
EudraCT No.: 2013-004025-88

CONFIDENTIAL
Status: Final
Page: 30 of 114

At least the first 2 treatment-requiring bleeding episodes should be treated in the presence of a qualified health care professional. If the patient cannot be brought quickly to the trial site, the trial site must be contacted for treatment instructions or transport. A severe bleeding episode should immediately be treated at home or at the local emergency room, and the trial site must be contacted for further instructions or transport. For severe bleeding episodes before the 2nd EDs the treatment must take place at the site.

In case of treatment requiring bleeding episodes prior to home treatment, these should immediately be treated at trial site. In case the bleeding episode occurs outside trial site opening hours, the bleeding episode should be treated according to local practice.

The need for a second dose of N8-GP should be evaluated within 8 hours of the initial dose. If two doses are not sufficient to treat the bleeding episode, and immediately in the case of a severe bleeding episode, the trial site must be contacted as soon as possible for further instructions and/or transport to the trial site for an unscheduled visit.

Total number of N8-GP doses and frequency of dosing for treatment of a bleeding episode is decided by the investigator based on the individual bleeding episode characteristics and haemostatic response to treatment, and/or based on local guideline or standard of practice. Dosing guidance may be provided at a scheduled or unscheduled visit at the clinic or by telephone contact to the trial site.

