If needed and decided by the Investigator, the initiation of the ITI can be delayed but it has to start within 6 months from the time of diagnosis of inhibitor. Inhibitor patients that commence ITI with N8-GP will follow an alternative treatment regimen and visit schedule (see Section 8.1.11). If the inhibitor disappears during the ITI (see Section 8.4.2.2, the patient should resume prophylaxis treatment as recommended in Section 5.3.2. For patients still with positive inhibitors after 12 months ITI, continued trial participation will be evaluated by the investigator and sponsor based on the level of inhibitors, within the predefined specifications of withdrawal criteria 8, see Section 6.4. However, if the inhibitor persists after 24 months of ITI, the patient will be withdrawn from the trial.

For patients who develop low titre and/or clinically insignificant inhibitors (< 5 BU), the dose level and dosing frequency of N8-GP will be decided by the Investigator based on clinical evaluation.

Protocol v 1 | 33 of 114

 Trial ID: NN7088-3908
 Version:
 1.0

 UTN: U1111-1148-1897
 Status:
 Final

 EudraCT No.: 2013-004025-88
 Page:
 34 of 114

Table 5–1 Intravenous N8-GP treatment

Indication	Dosage	Frequency
Pre-prophylaxis (pt. less than 24 months of age)	Approximately 60 U/Kg (50-75U/Kg)	On-demand or slow start prophylaxis (less than weekly dosing)
Prophylaxis – main phase	Approximately 60 U/Kg (50-75U/Kg)	Every 3 rd day, twice weekly or every 7 th day(±1 day)
Prophylaxis – extension phase	Approximately 60 U/Kg (50-75U/Kg)	Every 3 rd day, twice weekly, every 4 th day, every 5 th day, every 6 th day or every 7 th day(±1 day)
Mild/moderate bleeding episode	20-60 U/Kg	On-demand (breakthrough bleeding episodes)
Severe bleeding episode	40-75 U/Kg For treatment of severe/life- threatening bleeding episodes administration of higher doses of N8- GP is permitted at the investigator's discretion	On-demand
Minor surgery	40-75 U/Kg	In accordance with local standard of practice of the participating trial site
Major surgery, only allowed after 50 EDs	Recommended doses regimens will be provided when the N8-GP surgery trials completed	On-demand
Low titre inhibitor	Recommendation 60 U/Kg (50-75 U/Kg) for prevention and treatment of bleeding episodes	Dosing interval as needed
Maximum dose/day	200 U/Kg	Total maximum dose over 24 hours

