8.1.12.2 Home treatment of bleeding episodes

Bleeding episodes must be treated as soon as identified according to Table 5–1 and Section 8.6.

Patient's parents(s)/LAR(s) will be instructed by the investigator on how to treat their child for a bleeding episode at home and how to record this in the eDiary.

Protocol v 1 | 50 of 114

Page:

51 of 114

UTN: U1111-1148-1897 EudraCT No.: 2013-004025-88

The following procedures must be performed

- N8-GP administration for treatment of treatment requiring bleeding episodes, see Section 8.6
- Completion of the patient eDiary, including details of all bleeding episodes and N8-GP administrations (see Section 8.6).

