8.5 N8-GP administration

N8-GP will be administered while the patient is in a comfortable position according to Table 5–1.

During ED 1-2 with treatment at the trial site (V1 -V2):

The first 2 N8-GP doses should be administered at trial site by, or under direct supervision of an attending physician.

Trial injection kits (butterflies etc) will be provided by Novo Nordisk. Choice of butterfly or cannula for N8-GP injections is at the discretion of the investigator

The actual time of completion of the injection will be recorded and corresponds to trial time point = 0.

During ED 3-100 with treatment at trial site and at home (after V2):

Home treatment with administration of N8-GP can start after 2 EDs if the patient or the patient's parent(s)/LAR(s) are comfortable with the reconstitution and administration process. If not the drug administration can take place at site.

- Home treatment may be given by the patient's parent(s)/LAR(s) or a home nurse, as applicable.
- The injection should be performed as an i.v. bolus injection (approximately 2 min for an injection). The date and the actual time of completion of the injection must be recorded in the patient's eDiary.
- All treatment requiring bleeding episodes should be treated and registered independently of the on-going prophylaxis treatment regimen.
- If a bleeding episode occurs earlier at the same day as the planned prophylaxis, the dose should be registered for the bleeding episode and not as prophylaxis and the planned prophylaxis dose later the same day should be omitted. The dose for the treatment of bleeding episode on a prophylaxis day should be approximately 60 U/Kg, and then the prophylaxis dose should not be taken.
- When a prophylaxis dose has been taken and a bleeding episode occurs later the same day, the bleeding episode should be treated and registered independently of the prophylaxis dose.

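### Section 9.1 caps a single dose at 75 U/Kg in severe bleeds without exception, while the severe-bleed row of Table 5-1 permits higher doses

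*Combined protocol and SAP*

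**What the plan says.** **The cap.** Section 9.1 (Trial product) of version 1.0: "The maximum dose to be administered to a patient within 24 hours is 200 U/Kg, with a maximum individual dose of 75 U/Kg". The next sentence gives its setting: "These doses are only relevant in case of trauma, severe bleedings or surgery". No exception follows.

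**The permission.** The severe-bleed row of Table 5-1 gives 40-75 U/Kg in its dosage column. The same cell continues, for severe or life-threatening bleeds, in part: "threatening bleeding episodes administration of higher doses of N8- GP is permitted at the investigator's discretion". The last row of the table sets 200 U/Kg, labelled "Total maximum dose over 24 hours". It sets no general limit on an individual dose.

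Section 5.3.3 of version 1.0 gives 20-75 U/Kg for bleeds and then says: "For treatment of severe/life-threatening bleeding episodes administration of higher doses of N8-GP is permitted at the investigators discretion".

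**Where sites are sent for dosing.**
- Section 5.3.3: "For recommended dose levels see Table" 5-1.
- Section 8.1.12.2: "Bleeding episodes must be treated as soon as identified according to" Table 5-1 and section 8.6.
- Section 8.5: "N8-GP will be administered while the patient is in a comfortable position according to Table" 5-1.

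**Amendment 2.** The severe-bleed row keeps the permission and now ties it to repeated trough and recovery measurements. The entry for section 9.1 changes text on the volume drawn from a vial, mixing and solvent supply. The cap sentence is not among the changes shown. For patients with inhibitors, the amendment states a 75 U/kg single-dose limit alongside the 200 U/kg daily limit in sections 5.3.6, 5.3.6.1 and 8.1.11 and in a new high-titre row of Table 5-1.

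**The concern.** The cap and the permission cover the same situation, a severe bleed, and appear to give opposite answers for one dose above 75 U/Kg. Staff treating a severe or life-threatening bleed in a child enrolled below 6 years of age are directed to Table 5-1, which lets the investigator exceed the range. The product section does not.

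The same dose could therefore be recorded at one site as permitted and at another as a protocol deviation, which section 18 requires to be documented and explained. That consequence is an inference from the texts, but it is the ordinary result of two unreconciled limits in force together. What is at stake is clarity of an urgent dosing instruction and consistent deviation reporting, not the analysis of any endpoint.

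**Working it through.** There is no plan figure to reproduce. The check compares texts, with a little arithmetic to test the alternative reading.

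**Step 1. Set the texts side by side.**

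| Source | Single dose in a severe bleed | 24-hour total |
|---|---|---|
| Section 9.1, version 1.0 | at most 75 U/Kg, no exception | 200 U/Kg |
| Table 5-1, version 1.0 | 40-75 U/Kg, then higher permitted | 200 U/Kg |
| Section 5.3.3, version 1.0 | 20-75 U/Kg, then higher permitted | not stated |
| Table 5-1, Amendment 2 | 40-75 U/Kg, then higher permitted with trough and recovery guidance | 200 U/Kg |

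The 24-hour totals agree wherever they are stated. The single-dose entries do not.

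**Step 2. Is the conflict still live?** The permission in Table 5-1 is, because Amendment 2 attaches new wording to it. The cap appears to be, because no amendment in the file shows a change to it. Section 5.3.3 is less certain. Amendment 2 reprints its permission, but strike-through was lost when the text was extracted, so one cannot tell whether the sentence was kept. The conflict with Table 5-1 does not depend on it.

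**Step 3. Does one text override the other?** The pointers listed above direct sites to Table 5-1. None says that the table displaces 9.1, and 9.1 does not say that it limits the table.

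**Step 4. Could the permission mean repeated doses of at most 75 U/Kg each?** Inputs: the 40-75 U/Kg range and the 200 U/Kg daily maximum, both from Table 5-1.
- Two doses at the top of the range: 2 × 75 = 150 U/Kg, below 200.
- Three doses at the top: 3 × 75 = 225 U/Kg, above 200.
- Filling the daily maximum with in-range doses: 75 + 75 + 50 = 200 U/Kg, each dose between 40 and 75.

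The whole daily maximum can thus be reached without leaving the stated range. Section 5.3.3 of version 1.0 also separately leaves the number and frequency of doses for a bleed to the investigator. On this reading the permission would add almost nothing. Its position also counts against that reading: it sits in the dosage column, directly after a per-dose range ending at 75.

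**Step 5. Which patients are affected?** Amendment 2, section 5.3.6, applies the 75 U/kg single-dose limit to bleeds treated with N8-GP in patients who have developed inhibitors. Sections 5.3.6.1 and 8.1.11 and the high-titre row repeat it for immune tolerance induction. For these patients a specific rule exists. The unresolved case is mainly a severe bleed in a patient without inhibitors.

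**The case against.** The best opposing argument is that Amendment 2 points towards repeated dosing. It ties the permission to repeated trough and recovery measurements. Section 16.4.2.6 defines trough as activity just before an injection and recovery from the value 30 minutes after it, so repeated measurement suggests successive injections. Section 5.3.3 of version 1.0 also has the need for a second dose assessed within 8 hours. If the permission means more injections, each within the cap, there is no contradiction.

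This stands in part: the documents do not expressly exclude that reading. But monitoring of this kind suits larger individual doses as well as more of them, and Step 4 shows that the permission would then be close to redundant.

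A second argument is that Amendment 2 prints the 75 U/kg single-dose figure in several places, and section 8.7 recommends a maximum of 75 U/kg before major surgery, so the cap may be a general rule. Those statements cut both ways. The amendment states a single-dose limit expressly where it wants one, including in another row of the same table, but not in the severe-bleed row.

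It is also fair that practical exposure is limited. The site or investigator must be contacted for a severe bleed, exceeding the range is a discretionary decision, and the daily maximum applies either way. Finally, the consolidated later protocol versions are not in the file, and the amendments show excerpts only. These points limit the weight of the finding without removing it.

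**Conclusion.** The inconsistency is real and should be corrected. On the natural reading, a single dose above 75 U/Kg in a severe bleed is permitted by Table 5-1 and barred by section 9.1, with no stated order of precedence. This rests on two assumptions: that the permission refers to the size of an individual dose, and that the cap sentence survives in the consolidated protocol, as the amendments shown suggest.

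Four stronger readings might be inferred, and the documents do not support them:
- **A disputed range up to 200 U/Kg.** A reader might take 200 − 75 = 125 U/Kg, or 200 / 75 = 2.67 times the cap, as the size of the conflict. But 200 U/Kg is a 24-hour total, and no text contemplates giving it as one dose. The size of any excess dose is not stated.
- **A conflict for every patient.** The separate limits in Amendment 2 cover patients with inhibitors.
- **A current conflict with section 5.3.3.** This is certain only for version 1.0.
- **Harm to an endpoint or a known number of affected bleeds.** The documents give no count of severe bleeds, and no route to an endpoint effect is shown.

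**What to change.** Reconcile section 9.1 with the severe-bleed row of Table 5-1, and with section 5.3.3 if its permission is still in force, so that all state the same single-dose rule for severe or life-threatening bleeds. Check the result against the single-dose statements that Amendment 2 makes in sections 5.3.6, 5.3.6.1, 8.1.11 and 8.7 and in the high-titre row. If the permission was meant to cover repeated doses within the cap, the text should say so. Which rule is right is for the sponsor's clinicians, and this review takes no position on it.

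The cost is a wording change. It needs a protocol amendment and the usual approvals, since section 24 bars implementation before approval or a favourable opinion except to remove an immediate hazard. No new data, visits or analyses are needed.
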